Note: All visits scheduled during the controlled assessment period and during the extension period should occur within ±2 days of the scheduled date, relative to Visit 2 (Week 0).

Visit 11 must occur at least 10 weeks from final dose but no more than 12 weeks.

The Investigator and/or qualified study-site personnel will contact patients by phone at Week 2, Week 16, and Week 26 to discuss study compliance, address questions related to study medication, and review adverse events.

- All patients will have Visit 11 (Week 62/Study Termination) which is a follow-up visit occurring 10 weeks after the last dose administration at Visit 10 (Week 52).
- Following Visit 11 (Week 62/Study Termination), patients whose height increase is at least 5 mm between Visit 8 (Week 28) and Visit 11 (Week 62/Study Termination) will participate in an Extended Safety Follow-up Period. Patients who discontinue study medication prior to Visit 11 (Week 62) will also participate in the Extended Safety Follow-up Period, unless they have a height increase of less than 5 mm over a 6-month interval at study-site visits prior to discontinuation of study medication. Patients who do not have height assessments at study-site visits over a 6-month interval prior to discontinuation of study medication will enter the Extended Safety Follow-up Period.
- The Extended Safety Follow-up Period will continue for up to 3 years or until the increase in height between two 6 month interval visits is less than 5 mm (whichever comes first). No study medication will be administered during the Extended Safety Follow-up Period.

Target Patient Population

A total of 77 male or female children and adolescents of 10 to <18 years of age, diagnosed with type 2 diabetes mellitus and treated with diet and exercise alone or in combination with a stable dose of an oral antidiabetic agent (metformin and/or sulfonylurea [SU]) and/or insulin

for at least 2 months prior to screening, will be randomized into this study to yield 70 evaluable patients.

Key Inclusion Criteria

Each patient must meet the following criteria to be enrolled in this study.

1. Is a child or an adolescent of 10 to <18 years old, at Visit 1 (Screening)
2. Has been diagnosed with type 2 diabetes mellitus per American Diabetes Association diagnostic criteria
3. HbA1c of 6.5% to 11.0%, inclusive, in patients not taking insulin/SU, and of 6.5% to 12.0%, inclusive, in patients taking insulin/SU, at Visit 1 (Screening)

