3.1 Overall study design and flow chart

- This Phase 3, double-blind (controlled assessment period), randomized, multicenter, placebo-controlled parallel study is designed to examine the efficacy and safety of EQW compared to placebo (PBO) in adolescents with type 2 diabetes for 24 weeks.
- This study will assess safety and efficacy of EQW (as monotherapy and adjunctive therapy to oral antidiabetic agents and/or insulin).
- At least 40% and not more than 60% of the randomized patients must be females. At least 40% of patients should be recruited from areas with similar ethnicity and lifestyle to those of the European Union member states.
- Long-term safety and efficacy of EQW will subsequently be monitored for 28 weeks in the open-label, uncontrolled extension period (through Week 52).
- The study will be terminated at Visit 11 (Week 62/Study Termination) which will be a follow-up visit occurring 10 weeks after the last dose administration at Visit 10 (Week 52).
- This study will be conducted in 77 patients with type 2 diabetes treated with diet and exercise alone or in combination with a stable dose of oral antidiabetic agents and/or insulin for at least 2 months prior to screening. A schematic overview of the study design is presented in [Figure 1](#). During the controlled assessment period, approximately 77 patients will be randomly assigned in a 5:2 ratio to receive either EQW 2 mg (Group A) or PBO (Group B), to yield at least 70 evaluable patients: at least 50 patients in the exenatide and at least 20 patients in the PBO group.

- Following the 24-week controlled assessment period, patients assigned to the EQW 2 mg treatment (Group A) will continue to be treated with EQW 2 mg during the extension period (through Week 52). Patients randomized to PBO (Group B) will receive EQW 2 mg beginning at the start of the extension period, Week 25 through Week 52.
- In addition to receiving study medications, all patients will participate in a lifestyle intervention program encompassing diet and physical activity modifications following the signing of the informed consent and assent forms (Visit 1 [Week -2]) through the end of the extension period (Week 52).

Figure 1 Study Design

Abbreviations: EQW, exenatide once weekly; P, phone call

Note: All visits scheduled during the controlled assessment period and during the open-label extension period should occur within ± 2 days of the scheduled date, relative to Visit 2 (Week 0).

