5.7 Treatment compliance

The administration of all study drugs (including investigational products) should be recorded in the appropriate sections of the CRF.

The study drug dispensation as per visits has been summarized in Table 4.

Table 4 Study Drug Dispensation per Visits Schedule

Visit (week)	Exenatide/placebo vial 4-weeks kit. (24-Week Controlled assessment Period).	Exenatide vial 4-weeks kit (28-Week Extension Period).	Diluent 4-weeks kit
Visit 2 (Week 0)	1	N/A	1
Visit 3 (Week 4±2 days)	1	N/A	1
Visit 4 (Week 8±2 days)	1	N/A	1
Visit 5 (Week 12±2 days)	2	N/A	2
Visit 6 (Week 18±2 days)	2	N/A	2
Visit 7 (Week 24±2 days)	N/A	1	1
Visit 8 (Week 28±2 days)	N/A	3	3
Visit 9 (Week 40±2 days)	N/A	3	3
Visit 10 (Week 52±2 days)	N/A	N/A	N/A

Abbreviation: N/A=not applicable

Visit 2 (Week 0): At Visit 2, a 4-week supply of blinded study medication kits will be dispensed to all patients, according to their assigned treatment group.

Visit 3 (Week 4) and Visit 4 (Week 8): At Visit 3 and Visit 4 an additional 4-week supply of study medication will be dispensed to all patients, according to their assigned treatment group.

Visit 5 (Week 12) and Visit 6 (Week 18): At Visit 5 and Visit 6 an additional 8-week supply of study medication will be dispensed to all patients, according to their assigned treatment group.

Visit 7 (Week 24): At Visit 7 a 4-week supply of open label study medication will be dispensed to all patients.

Visit 8 (Week 28) and Visit 9 (Week 40): At Visit 8 and Visit 9 a 12-week supply of open label study medication will be dispensed to all patients.

Visit 10 (Week 52/End of Treatment): Patients to return all used and unused study medication to the study site.

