6.2.3.10 Visit 10 (Week 52) - End of Treatment or Early Termination

Prior to Visit 10 (Week 52) or Early Termination, patients will have fasted overnight (≥ 8 hours).

All patients will undergo the following procedures:

- Review of concomitant medication and AEs
- Physical examination will be performed
- Body weight, height, and vital signs will be measured
- Assessment of Tanner pubertal stage
- Injection site reaction assessment will be performed
- Urine will be collected for:
 - Pregnancy test (females only) (only for Visit 10 [Week 52])
 - Urinalysis
 - Urinary albumin creatinine ratio
 - N-telopeptide.
- Blood samples will be collected for:
 - Serum pregnancy test (β hCG) for all female patients (only for early termination visit)
 - Chemistry and hematology
 - HbA1c
 - Fasting plasma glucose
 - Fasting insulin
 - Calcitonin
 - Pancreatic amylase and lipase
 - Fasting lipids (TC, HDL-C, LDL-C, and TG)
 - TSH, FSH, LH, total testosterone, SHBG, estradiol, free T4, prolactin, cortisol, IGF-1, DHEAS, and bone specific alkaline phosphatase

- CEA
- Measurement of antibodies to exenatide
- Measurement of plasma exenatide.
- Bone age assessment by X-ray
- Patients will have a study medication compliance review
- Patients will be asked to return used/unused study medication.

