6. STUDY DURATION

The total duration of the substudy will be approximately 62 weeks; the substudy will be initiated at baseline Visit 2 (Week 0) and concluded at Visit 11 (Week 62/Study Termination), approximately 10 to 12 weeks following the discontinuation of study medication at Visit 10 (Week 52).

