1.2 Study design

This Phase 3, double-blind (controlled assessment period), randomized, multicenter, placebo-controlled parallel study is designed to examine the efficacy and safety of EQW compared to PBO in adolescents with type 2 diabetes for 24 weeks.

This study will assess safety and efficacy of EQW (as monotherapy and adjunctive therapy to oral antidiabetic agents and/or insulin). A schematic overview of the study design is shown in [Figure 1](#). See D5551C00002 Clinical Study Protocol version 4.0, dated 14th December 2017 (CSP) Table 1 for the schedule of activities planned.

The study includes a 24-week, controlled assessment period, during which patients will receive study medication in accordance to their randomized treatment group, followed by a 28-week, open-label, uncontrolled extension period in which all patients will receive EQW.

At least 40% and not more than 60% of the randomized patients must be females. At least 40% of patients should be recruited from areas with similar ethnicity and lifestyle to those of the European Union member states.

[figure not shown]
Approximately 77 patients will be randomly assigned across 2 treatment groups in a 5:2 ratio to receive either subcutaneous (SC) administration of EQW 2 mg (Group A) or PBO (Group B), respectively, with at least 50 evaluable patients in the EQW and at least 20 evaluable patients in the PBO group.

In addition to receiving study medications, all patients will participate in a lifestyle intervention program encompassing diet and physical activity modifications from Visit 1 (Week -2) to Visit 10 (Week 52). If patients are taking concomitant antidiabetic medication, they should administer their usual concomitant antidiabetic medication therapy at approximately the same time each day throughout the study.

Following the 24-week controlled assessment period, all patients will enter the 28-week extension period. During the 28-week extension period, all patients will receive EQW 2 mg for 28 weeks up to Visit 10 (Week 52/End of Treatment). The patients will return to the study site at 4- or 12-week intervals for safety, efficacy, Pharmacodynamics, and PK assessments and will complete study termination procedures at Visit 11 (Week 62/Study Termination).

All patients will complete study termination procedures Visit 11 (Week 62/Study Termination) which is a follow-up visit occurring 10 weeks after administration of the last dose of EQW at Visit 10 (Week 52).

Figure 1: Study Design

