Abbreviations: EQW, exenatide once weekly; P, phone call

Note: All visits scheduled during the controlled assessment period and during the open-label extension period should occur within ± 2 days of the scheduled date, relative to Visit 2 (Week 0).

Visit 11 must occur at least 10 weeks from final dose of study medication but no more than 12 weeks.

The Investigator and/or qualified study-site personnel will contact patients by phone at Week 2, Week 16, and Week 26 to discuss study compliance, address any questions related to study medication, and review adverse events.

Note: The first dose of open-label EQW during the extension period will be given at the Week 24 visit.

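### The last open-label dose is placed at Week 52 in some text and implied at Week 51 by other text; if it is Week 51 or earlier, the SAP's last-dose-plus-7-days rule can drop protocol-compliant Week 52 safety values from the summaries

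*Protocol*

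**What the plan says.** Four places put the last open-label exenatide (EQW) dose at Week 52. Protocol 3.1 describes Visit 11 as a "follow-up visit occurring 10 weeks after the last dose administration at Visit 10 (Week 52", and the synopsis says the same. Protocol Appendix F section 6 dates Visit 11 from the time "following the discontinuation of study medication at Visit 10 (Week 52". SAP 1.2 counts the 10 weeks from "administration of the last dose of EQW at Visit 10 (Week 52". Protocol 3.1 also gives placebo patients EQW "beginning at the start of the extension period, Week 25 through Week 52".

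Other text points to Week 51. The note under Figure 1 in SAP 1.2 reads "The first dose of open-label EQW during the extension period will be given at the Week 24 visit", and SAP 1.2 gives 28 weeks of open-label treatment. Protocol 5.7 (Table 4) dispenses one 4-week kit at Visit 7, then "At Visit 8 and Visit 9 a 12-week supply of open label study medication will be dispensed to all patients"; nothing is dispensed at Visit 10. The procedure list in Protocol 6.2.3.10, headed "Visit 10 (Week 52) - End of Treatment or Early Termination", includes return of medication but no dosing step, whereas the lists for Visits 3 to 9 include on-site dosing where applicable.

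The analysis rules are these:

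- SAP 3.6.5.2 ends the extension period for visit-based safety parameters 7 days after the last open-label dose. The Treatment period ends the same way.
- In SAP 4.3.3, the Week 52 windows for vital signs, Tanner stage, hormones and laboratory tests (Tables 3.5 and 3.7 to 3.9) close on the last day of that period.
- SAP 4.3.1 presents Week 62 by visit label only.
- For efficacy, SAP 3.6.5.1 ends the extension period at the Week 52 visit.
- Protocol 3.1 allows visits, and Protocol 5.5.2 allows doses, 2 days either side of schedule, both counted from Visit 2.

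**The concern.** The last-dose date fixes the last day of the safety extension period. If that date is a week before Visit 10, the period nominally ends on the scheduled Visit 10 day itself, and a visit one or two days late, which the protocol allows, falls outside it. The efficacy period has no such problem, because it ends at the visit. The Week 24 safety assessments of patients who continue are also protected: SAP 3.6.5.2 deliberately keeps them in the controlled period.

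At stake are the Week 52 by-visit summaries and the extension shift tables for chemistry, hematology, urinalysis, hormones, calcitonin, amylase, lipase, CEA, Tanner stage and safety vital signs. Long-term safety is a study objective, and changes in calcitonin, amylase and lipase to Week 52 are named safety variables (SAP 3.4). The loss would matter most for placebo patients who switched to EQW. By Protocol 6.2.3.9, Visits 8 and 9 draw blood only for HbA1c, plus testosterone and SHBG at Week 40. Visit 10 is therefore their only scheduled on-EQW sample for chemistry, hematology, calcitonin, amylase, lipase, CEA and TSH.

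**Working it through.** **Day numbering.** Day = 1 + 7 × week. This reproduces the SAP target days 29, 57, 85, 127, 169, 197, 281 and 365 for Weeks 4, 8, 12, 18, 24, 28, 40 and 52. Visit 10 is Day 365, allowed on Days 363 to 367.

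**Number of open-label doses.** Table 4 gives 1 + 3 + 3 = 7 kits, and each kit holds 4 doses (Protocol 5.5.1), so 28 doses.

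- Weeks 24 to 51: 28 doses.
- Weeks 25 to 52: 28 doses.
- Weeks 24 to 52: 29 doses.

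Table 4 alone fits either of the first two. Joined to the SAP's Week 24 start, it gives a last dose at Week 51: Day 169 + 7 × 27 = 358. A Week 52 dose would then be the 29th. The protocol's range for placebo patients agrees with Week 51 only if it means the 25th to the 52nd week of treatment (Days 169 to 364).

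**End of the safety extension period.** Nominal Week 51 dosing: 358 + 7 = Day 365. Visit 10 on Days 363 to 365 is kept; Days 366 and 367 are not. With the 2-day dosing tolerance:

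| Last dose (Week 51) | Period ends | Allowed Visit 10 days excluded | Count |
|---|---|---|---|
| Day 356 | Day 363 | 364, 365, 366, 367 | 4 |
| Day 357 | Day 364 | 365, 366, 367 | 3 |
| Day 358 | Day 365 | 366, 367 | 2 |
| Day 359 | Day 366 | 367 | 1 |
| Day 360 | Day 367 | none | 0 |

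Total: 10 of 25 day pairs.

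**Other cases.**

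- Last dose at Week 52 (Days 363 to 367): the period ends on Days 370 to 374, and 0 of 25 pairs are excluded.
- Week 51 dose missed without discontinuation, so last dose at Week 50 (Days 349 to 353): the period ends on Days 356 to 360, and 25 of 25 pairs are excluded. Such a patient can still meet the completer definition in SAP 3.6.5.5.

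**Visit 11 does not settle the date.** Week 62 is Day 435. (435 − 365)/7 = 10 weeks and (435 − 358)/7 = 11 weeks; both satisfy the 10-to-12-week rule.

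**The case against.** The strongest reply is that the only last-dose date either document states is Visit 10 (Week 52), and on that date nothing is lost. No text names Week 51. The blinded supply is 1 + 1 + 1 + 2 + 2 = 7 kits, or 28 doses, enough to cover a blinded dose at Week 24. Open-label dosing over Weeks 25 to 52 would therefore be consistent with Table 4. The Visit 10 procedure list is shared with early termination, so its silence on dosing is weak evidence. This stands as far as it goes: Week 51 is an inference. But it leaves the SAP inconsistent with itself, because a Week 24 start and a Week 52 last dose need 29 open-label doses and 28 are dispensed.

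The 7-day cut-off is also a deliberate on-treatment rule. The SAP amendment history for 20 May 2020 says the windows were set so that completers and early discontinuers are handled alike. That is a reasonable aim, and the fix gives up some of it. It does not follow that an in-window Week 52 visit was meant to be discarded.

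There is partial cover elsewhere. Visit 11 repeats chemistry, hematology, calcitonin and antibodies, and the laboratory summaries include that follow-up. These are off-drug values, and amylase, lipase, CEA and TSH are not repeated. Blood pressure and body weight are kept as efficacy variables. The instruction to select values within the study period first sits in the efficacy section (SAP 4.3.1), but SAP 4.2.4.4 applies that section to laboratory data, and the safety tables close on the same day anyway.

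**Conclusion.** The inconsistency is real and the consequence is conditional. If the last dose is at Week 51 or earlier, the SAP excludes visit-based safety values from allowed Visit 10 dates more than 7 days after that dose: Days 366 and 367 at nominal dosing, and all allowed dates if the Week 51 dose is missed. If the last dose is at Visit 10, nothing is excluded. The number of patients affected depends on dose and visit dates that the documents do not give, and may be zero. Efficacy, adverse events, potential Hy's Law (which SAP 4.2.4.3 extends to follow-up), listings and the 24-week comparison are unaffected.

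Four stronger readings are tempting and not supported:

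- That Week 51 is simply the SAP's schedule. SAP 1.2 itself states Week 52.
- That 10 of 25 pairs means 40% of patients lose their Week 52 values. The pairs are unweighted counts of allowed days, not probabilities.
- That Week 52 antibody results are shown to be lost. Their summary is limited to the treatment period (SAP 4.2.4.6), but no visit-window table covers them, so their handling is unspecified.
- That the Drug Administration row of Protocol Table 1 decides the date. The row is broken in the available text and supports neither side.

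The change is worth making before database lock because it is cheap and removes the dependence on an unsettled date.

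**What to change.** In SAP 3.6.5.2, for visit-based safety parameters in extension treatment completers (as defined in SAP 3.6.5.5), end the extension period on the later of the last open-label dose plus 7 days and the Visit 10 date. Use the same end date in the Treatment period definition. Keep last dose plus 7 days for patients who stop EQW early, and leave the adverse event, hypoglycemia and concomitant medication windows as they are. Tables 3.5 and 3.7 to 3.9 need no edit, since they refer to the last day of the period. If the last dose is in fact at Visit 10, the sentence changes nothing.

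Record the intended last-dose week in SAP section 5, which already corrects protocol wording on visit intervals, and align SAP 1.2. The synopsis, Protocol 3.1 and Appendix F section 6 can be corrected at the next amendment, since Protocol 8.5 may require ethics committees to be told or to approve.

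The cost is one sentence, a matching end date and a note, with no added patients, visits or samples. The downside is that completers and early discontinuers no longer share one rule. Some Week 52 values would also be taken longer after the last dose: up to 367 − 356 = 11 days with a Week 51 dose, and 363 − 353 = 10 to 367 − 349 = 18 days (nominally 365 − 351 = 14) if that dose is missed.

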3.2 Study duration

Total study duration will be approximately 67 weeks (excluding the Extended Safety Follow-up Period), including up to a 5-week screening period, a 24-week controlled assessment period, and a 28-week extension period, and a 10-week post-treatment follow-up period. The beginning of the treatment period should occur within 35 days following screening.

3.3 Rationale for study design, doses and control groups

This Phase 3 study is being conducted with the primary objective to compare the therapeutic efficacy, safety, and tolerability of EQW compared to placebo following 24 weeks of treatment. In addition, the study is designed to evaluate the long-term efficacy and safety of EQW following 28 weeks in an open-label, uncontrolled extension period. The study design and primary/secondary objectives reflect those recommended to evaluate the efficacy, safety, and tolerability of EQW in children and adolescent patients with type 2 diabetes.

3.3.1 Study design and regulatory requirement

A previous randomized, placebo-controlled, single-blind, dose-escalation crossover study (Study 2993-124) examined the PK, PD, safety, and tolerability of exenatide BID (2.5 and 5 µg) in adolescents between the ages of 10 and 16 with type 2 diabetes and an average body mass index (BMI) of 32.5 kg/m² (23.2 to 40.8 kg/m²). Consistent with clinical trials in adults, 5 µg exenatide nearly eliminated postprandial glucose excursions in adolescents. This study, and the results of previous studies with EQW conducted in adults, demonstrated that, in general, exenatide was well tolerated with a safety and efficacy profile that was comparable to that observed in adults (Malloy et al, 2009).

Given the decreased patient burden of once weekly injections, and the favorable efficacy and safety profile of EQW, the next step in the clinical development would be a Phase 3 study to demonstrate that this treatment may prove to be a useful adjunct therapy in adolescents with type 2 diabetes. The current study will enroll either patients treated with diet and exercise alone or in combination with a stable dose of an oral antidiabetic agent (metformin and/or SU) and/or insulin for at least 2 months prior to screening.

3.3.1.1 Extended Safety Follow-up Period

Following Visit 11 (Week 62/Study Termination), patients whose height increase is at least 5 mm between Visit 8 (Week 28) and Visit 11 (Week 62/Study Termination) will participate in an Extended Safety Follow-up Period. Patients who discontinue study medication prior to Visit 11 (Week 62/Study Termination) will also participate in the Extended Safety Follow-up Period, unless they have a height increase of less than 5 mm over a 6-month interval at study-site visits prior to discontinuation of study medication. Patients who do not have height assessments at study-site visits over a 6-month interval prior to discontinuation of study medication will enter the Extended Safety Follow-up Period. The Extended Safety Follow-up Period will continue for up to 3 years or until the difference between two 6-month interval visits is less than a 5 mm increase (whichever comes first). No study medication will be

administered during the Extended Safety Follow-up Period. Blood samples will be collected for calcitonin and carcinoembryonic antigen (CEA) laboratory measurements. Details of the Extended Safety Follow-up Period are provided in [Appendix E](#).

